11.3.1.5 Submitting an Expedited Safety Report to the IRB (Central or Local)

Any suspected unexpected serious adverse reaction (SUSAR) warrants expedited reporting. In addition, any unexpected SAE related to a subject's participation in the study (or conduct of study), regardless if the study drug was administered, will be evaluated by Global Pharmacovigilance and Risk Management (GPRM) to determine if expedited reporting is required. For example, an unexpected, serious and severe reaction which could be associated to the study procedures, and which could modify the study conduct requires expedited reporting. Each expedited safety report will routinely include a brief cover memorandum, the completed MedWatch Form FDA 3500A or Council for International Organizations of Medical Sciences I Form, a clinical analysis of the event with any similar events that have occurred with the product, and any additional pertinent information recommended by the study Medical Monitor. Once the report is compiled by GPRM, the site Investigator must submit the expedited safety report to the local IRB/EC within the required reporting timeframe. Follow-up reports should be submitted when requested or when pertinent information becomes available. The site principal Investigator must retain a complete copy of each expedited safety report as it was submitted to the IRB. It is important that the principal Investigator review these expedited reports, as they contain safety information that may be relevant to each of the participating subjects.

11.3.2 Pregnancy

All female subjects of childbearing potential must use an effective method of birth control during the course of the study, in a manner such that risk of contraceptive failure is minimized. Abstinence is allowed as a birth control method.

Before enrolling a female subject of childbearing potential in this clinical study, the investigator must review the following information about study participation:

- Informed consent/assent requirements.
- Contraceptives in current use.

Following review of this information and appropriate counseling for the subject and their parent/legal guardian, the investigator or designee and the subject and parent/legal guardian must sign the assent/informed consent before study enrollment.

During the study, all female subjects of childbearing potential should be instructed to contact the investigator immediately if they suspect they might be pregnant (eg, missed or late menstrual period).

If a subject or investigator suspects that the subject may be pregnant prior to study enrollment, the study drug must be withheld until the results of laboratory pregnancy testing are available. If pregnancy is confirmed, the subject must not receive study drug and must not be enrolled in the study. If pregnancy is suspected while the subject is receiving study treatment, the study drug

must immediately be withheld until the result of pregnancy testing is known. If pregnancy is confirmed, the study drug will be permanently discontinued and the subject will be followed until the pregnancy comes to term. A Pregnancy Report form will be submitted to the sponsor, initially and at the end of the pregnancy, which includes the outcome of the pregnancy and any complications occurring during the pregnancy or the delivery.

12 Statistics

12.1 Assessment of Safety

12.1.1 Adverse Events

All AEs that occur during the study will be recorded and classified using the Medical Dictionary for Regulatory Activities (MedDRA). Treatment-emergent adverse events (TEAEs) are those AEs that occur or worsen on or after the date of first study drug application. All TEAEs will be summarized by the number of subjects reporting each TEAE, the associated system organ class and preferred term, the severity, and the relationship to study drug for the safety, PK, and non-PK populations. Each subject will be counted only once within a system organ class or a preferred term using the event with the greatest severity or causality, respectively, within each category.

All SAEs will be summarized by the number of subjects reporting each SAE, the associated system organ class and preferred term, the severity, and the relationship to study drug for the safety, PK, and non-PK populations.

All information pertaining to AEs noted during the study will be listed by subject and will include the verbatim term given by the investigator, the associated system organ class and preferred term, the start and stop (if stopped) dates, the seriousness, and the severity of the event. Additionally, any action taken with the study drug, any corrective treatment administered, the outcome, and the relationship to study drug as well as a list of subjects who prematurely discontinue from the study due to an AE will be provided.

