11.1.1 Screening Visit (Visit 1, Up to Day -42)

After signing the informed consent/assent, subjects will undergo the screening procedures to confirm eligibility to participate in the study.

Newly screened PK subjects will decide at the time of signing consent whether they will consent to the 4-Week trial or participate in the 52-Week trial.

Note: *Subjects that consent to 4 -Week trial will not be allowed to extend their study consent to 52 weeks. Subsequently, PK subjects who consent to the 52-Week trial will be considered discontinued/Early Terminated if he/she discontinues prior to the Week 52 visit.*

The following procedures will be conducted at this visit:

1. Review and explain the nature of the study. Provide a visit schedule with the length of each visit to ensure that the subject can meet the requirements and has adequate transportation.
2. Obtain verbal and written informed consent/assent from the subject and the subject's parent(s) or legal guardian(s) prior to performing any study-related procedures. Provide signed copies of the consent and assent forms to the subject/parent(s) or legal guardian(s).
3. Obtain photography consent/assent from subject and/or the subject's parent(s) or legal guardian(s).
4. Assign a 6-digit study number, which includes the 3-digit investigational center number plus a unique 3-digit subject number beginning with 001 (eg, 001-001, 001-002, 001-003). Numbers must be assigned in chronological order.
5. Record subject's demographic information (sex, date of birth, age, ethnicity, and race).
6. Record subject's medical history including diabetes history.
7. Collect a detailed history of onychomycosis, including an estimated start date of infection, duration of current infection in the potential target great toenail, and all previous therapies used for onychomycosis treatment.
8. Review all prior medications (those used within 30 days prior to the Screening Visit) and previous antifungal medications used by the subject, including any recent over-the-counter topical treatments (those used within 60 days prior to the Screening Visit).
9. Review inclusion/exclusion criteria.

10. Examination of toenails for clinical presence of onychomycosis in at least 1 great toenail, within the definition of eligibility criteria. For subjects in the PK population, both great toenails and 4 other toenails must meet eligibility criteria
11. Examination of all other toenails for presence or absence of onychomycosis on each toenail.

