Note: PK subjects exiting the study on Day 29 (consented to only the 4-Week trial), the following procedures will be conducted in addition to the procedures listed above.

11. Collect blood and urine samples for routine safety laboratory analysis (hematology, serum chemistry, and urinalysis). Process and ship the samples to the central safety laboratory per instructions provided in the laboratory manual.
12. Measure height and weight.
13. Conduct an abbreviated physical examination (excluding urogenital/reproductive systems).

For subjects in the PK subset at Visit 3 only:

- Collect a predose blood sample after all other study procedures are completed.
- Apply the study drug to all 10 toenails at the investigational center within 1 hour after collecting the predose blood sample.
- Collect postdose blood samples at approximately 2 hours (\pm 5 min), 4 hours (\pm 5 min), and 12 hours (\pm 15 min) after study drug application.
- Instruct the subject to return the following morning for their 24-hour blood sample (Visit 3A (Day 29). Subject will not dose on the evening of Day 28.

11.1.4 Visit 3A (Week 4, Day 29) - Additional Visit for Subjects in the PK Subset

The following procedures will be conducted at this visit:

1. Record any AEs (query subject "Are there any changes in your health?").
2. Record local skin reaction scores reported by the subject.
3. Review concomitant medications.
4. Collect a blood sample 24 hours (\pm 30 min) after study drug application at Visit 3.
5. Obtain 1 bottle of study drug and weigh the bottle, complete the label and drug log, and dispense the bottle to the subject and their parent/legal guardian. Review the new dosing instructions with the subject (application to only the target great toenail and to any other affected toenails) and provide a copy of new dosing instructions to the subject.
6. Dispense a new diary that includes the new dosing instructions.

Note: PK subjects who consented to only the 4 Week trial will exit the study on Day 29. Drug and subject diary will not be dispensed and urine pregnancy test will not be collected at this visit.

11.1.5 Schedule the PK subset subject (if consented to the 52-Week trial) for the next study visit. Visit 5 (Week 12 [\pm 5 days]), Visit S (Week 24 [\pm 5 days]), Visit 11 (Week 36 [\pm 5 days])

Visits are to be scheduled in reference to Visit 2 (Baseline).

The following procedures will be conducted at these visits:

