11.3.1.4 Procedures for Reporting Adverse Events and Serious Adverse Events

The period of observation for collection of AEs extends from the time the subject and parent/legal guardian gives informed consent/assent until the last study visit or discontinuation from the study. The first concern will be the safety of the subject, and appropriate medical intervention will be made.

The Investigator or designee will elicit reports (ie, via direct questioning, observation, clinical evaluation) of AEs from the subject at each study visit and record all AEs. The Investigator will document the dates of onset, progress, outcome, and resolution of such AEs. The Investigator will also provide an assessment of all AEs as to the severity, causal relationship to study drug, and causal relationship to study protocol.

It is the investigator's responsibility to document all AEs that occur during the study. The AEs should be documented as a single medical diagnosis. When this is not possible, the AE should be documented in terms of signs and/or symptoms observed by the investigator or reported by the subject and/or their parent/legal guardian at each study visit.

All AEs occurring after the subject and their parent/legal guardian signs the assent/informed consent through the last study visit must be reported, regardless of whether or not the AEs are considered drug-related. All AEs, whether in response to a query, observed by the study site personnel, or reported spontaneously by the subject and/or their parent/legal guardian, will be recorded.

At each visit during the study, the subject will be assessed for the occurrence of new and ongoing AEs. Cutaneous tolerability signs and symptoms that result in the subject's requiring a concomitant therapy or discontinuation from the study will be reported as an AE. The following data will be collected on all AEs and recorded on the appropriate eCRF:

- Event name (diagnosis preferred, if unknown, record the signs/symptoms).
- Onset date and end date.
- Maximum intensity (severity).
- Seriousness.

- Action taken regarding study drug.
- Corrective treatment, if given.
- Outcome.

In addition, the investigator's assessment of causality will be recorded.

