Any SAE must be reported to the Sponsor, independent of the circumstance or suspected cause, within 24 hours from the time the event was reported to the Investigator. All SAEs experienced from the date of consent through at least 30 days after the last dose of study drug must be reported to the Sponsor regardless of the relationship to the study drug or the protocol. For events occurring beyond the minimum 30-day period after the last dose of study drug, or for any timeframe afterward deemed medically significant, only SAEs considered related to the study drug should be reported promptly to the Sponsor.

Within 24 hours of notification the Investigator will fax or email a completed Serious Adverse Event Report to the Sponsor:

MedTrials Safety:

Fax: [REDACTED]

**Please follow up with an email notification to
[REDACTED] to confirm the faxed submission.

Investigators should not wait to receive additional information to document the event before notifying the sponsor of an SAE. If only limited information is initially available, follow-up reports are required. If the Investigator becomes aware of any new information regarding a SAE (ie, resolution, change in condition, or new treatment), a new SAE Form must be completed and faxed/mailed to the Sponsor within 24 hours. The original SAE form is not to be altered. The report should be marked as a "follow-up report" and describe whether the event has resolved or continues and how the event was treated. Additional relevant information such as hospital records and autopsy reports should be provided to the sponsor as soon as they are available.

Should the investigator become aware of an SAE (regardless of its relationship to investigational product) that occurs within 30 days after stopping the study drug, the SAE must be reported in accordance with procedures specified in this protocol.

The investigator should take all appropriate measures to ensure the safety of the subjects, notably he/she should follow a subject with an SAE until the event has resolved or the condition has stabilized. This may imply that follow-up will continue after the subject has left the study, and that additional investigations may be requested by the sponsor.

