12.1.3 Clinical Laboratory Tests

Results of safety laboratory parameters will be summarized at each study visit using descriptive statistics or frequencies and percentages, as appropriate, for the safety, PK, and non-PK populations. Changes from baseline in safety laboratory values will be summarized by treatment group at Week 48 using descriptive statistics. In addition, changes from baseline in safety laboratory values will be summarized using shift tables according to normal ranges.

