12.1.4 Vital Signs

Results of vital sign measurements will be summarized at Weeks 12, 24, 36, and 48 using descriptive statistics or frequencies and percentages, as appropriate, for the safety, PK, and non-PK populations. Changes from baseline in vital sign measurements will be summarized at these visits.

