12.8.1 Analysis Populations

All subjects who receive at least 1 confirmed dose of study drug will be included in the safety population.

All subjects in the PK subset who receive at least 1 confirmed dose of study drug and have any PK data on Days 28 and 29 will be included in the PK population.

All safety population subjects who are not in the PK subset will be included in the Non-PK population.

12.S.2 Sample Size Determination

Approximately 60 subjects will be enrolled and receive treatment with study drug.

Approximately 20 of the 60 subjects will be enrolled in the PK subset. These sample sizes were based on PK and clinical considerations; no formal sample size calculation was performed. The numbers of planned subjects are considered adequate for determining the safety profile and the PK parameters of efinaconazole in a pediatric population of subjects aged 6 to 16 years 11 months with mild to severe onychomycosis of the toenails.

12.S.3 Handling of Missing Data

No imputations will be made for analyses of safety or PK endpoints. The efficacy endpoints at Week 52, which are used to assess treatment compliance will have missing data imputed with the last observation carried forward (LOCF) for non-PK population analyses.

12.S.4 Multicenter Issues

The study will be conducted at multiple investigational centers in the US and the Caribbean with the intention of pooling the results for analysis.

12.S.5 Multiplicity Issues

Not applicable.

12.S.6 Windowing Rules

The timing of all study visits is relative to the Baseline (Day 1) visit. Visit 3 (Week 4) should occur within 5 days of Day 28, (except for the PK-subset; Visit 3 should occur within 1 day of Day 28) and Visit 3A (Week 4) should occur 1 day after Visit 3. The Week 8 and all subsequent visits should occur within 5 days of the targeted times.

13 Quality Control and Quality Assurance

This study will be conducted under the sponsorship of Valeant, in conformation with all appropriate local and federal regulations as well as ICH guidelines.

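### The Day 29 exit for PK subjects was not carried through the protocol: sections conflict on Day 28 vital signs, Day 28 change summaries are incomplete, and TEAE counts can mix about 29 days with 52 weeks

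*Combined protocol and SAP*

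**What the plan says.** All references are to the current protocol version, the one that contains the 4-week option.

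**The exit.** Section 11.1.1: "Newly screened PK subjects will decide at the time of signing consent whether they will consent to the 4-Week trial", or to the 52-week trial. Section 11.1.4 (Visit 3A): "PK subjects who consented to only the 4 Week trial will exit the study on Day 29". The protocol does not say how many of the roughly 20 PK subjects are expected to choose 4 weeks.

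**Day 28 vital signs.** The synopsis (Criteria for evaluation, Safety) and Table 1 (vital signs row, footnote t) call for them in 4-week PK subjects. The Visit 3 lists in 11.1.3 and the schedule in 11.2.3 do not mention them.

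**Summaries.** Section 12.1.4: "Results of vital sign measurements will be summarized at Weeks 12, 24, 36, and 48", with changes from baseline at those same visits. The synopsis (Statistical Methods, Safety) instead promises vital sign and laboratory summaries at every study visit. Section 12.1.3 also summarises laboratory results at each visit, but for change it says: "Changes from baseline in safety laboratory values will be summarized by treatment group at Week 48 using descriptive statistics". It adds shift tables without naming a visit.

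**Adverse events.** Section 12.1.1: "All TEAEs will be summarized by the number of subjects reporting each TEAE", for the safety, PK and non-PK populations. Under 11.3.1.4, AEs are collected "until the last study visit or discontinuation from the study". For serious events: "All SAEs experienced from the date of consent through at least 30 days after the last dose of study drug must be reported". Section 12.8.1 defines the populations without reference to consented duration; for the third one: "All safety population subjects who are not in the PK subset will be included in the Non-PK population".

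**The concern.** Once some PK subjects leave at Day 29, each section that fixes a visit schedule or a summary visit has to account for them. Several do not.

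The collection gap matters most. Baseline vital signs are taken before the first dose, and the Day 29 procedures contain no vital signs. Day 28 is therefore the only on-treatment vital sign assessment that 4-week subjects could have, and it comes at the end of maximal-use treatment. If a site works from 11.1.3, the measurement may be lost for good, and no analysis plan can restore it.

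The summary gap is smaller. For a 4-week subject, change from baseline under maximal use has no specified descriptive summary for laboratory values, and for vital signs the text contradicts itself.

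The TEAE point concerns interpretation. The first primary objective is safety over 48 weeks. A crude count of subjects with an event depends on how long each subject is observed, and the Safety and PK columns may combine two planned durations without showing it.

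**Working it through.** **1. Day 28 vital signs in 4-week PK subjects**

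| Place | Listed? |
|---|---|
| Synopsis, Criteria for evaluation | Yes |
| Table 1, vital signs row, footnote t | Yes, 4-week PK subjects only |
| 11.1.3, items 1–10 (all subjects) | No |
| 11.1.3, items 11–13 (4-week PK subjects) | No: laboratory samples, height and weight, physical examination |
| 11.1.4 (Day 29) | No |
| 11.2.3 | No: Baseline, Weeks 12, 24, 36, 48/Early Termination |

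Two places require the measurement, and the two sections a site would work from omit it.

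**Day 28 laboratory samples.** The synopsis (Criteria for evaluation), 7.2, Table 1 and 11.1.3 item 11 agree that these are for 4-week PK subjects. The synopsis Methodology paragraph states Day 28 sampling with no restriction, and 11.2.2 does not mention Day 28. Collection is at little risk here, because item 11 names the samples.

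**2. Day 28 summaries**

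- Vital signs: the synopsis covers every visit; 12.1.4 covers Weeks 12, 24, 36 and 48. This is a direct conflict.
- Laboratory: Day 28 values fall under the by-visit summary and may enter the shift tables. Only the descriptive change from baseline at Day 28 is unspecified.

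**3. TEAE counts**

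The protocol has no sample size calculation and no stated TEAE rate, so there is no figure to reproduce. What follows is an illustration.

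Inputs from the protocol: about 60 subjects, about 20 of them PK, hence 60 − 20 = 40 non-PK; AE observation to about Day 29 or to Week 52 (52 × 7 = 364 days).

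Assumptions: true 52-week risk p = 0.10 in every subject; constant and equal hazard; k PK subjects on the 4-week plan, k = 5 or 10.

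- Share of follow-up: 29/364 = 0.0797, about 8.0%.
- Risk by Day 29: r = 1 − (1 − p)^(29/364) = 1 − 0.9^0.0797 = 0.00836.
- PK column = [(20 − k)p + kr]/20. k = 5: (1.5 + 0.0418)/20 = 7.7%. k = 10: (1.0 + 0.0836)/20 = 5.4%.
- Safety column = [(60 − k)p + kr]/60. k = 5: (5.5 + 0.0418)/60 = 9.2%. k = 10: (5.0 + 0.0836)/60 = 8.5%.
- Non-PK column = 10%.

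Serious events have a longer window. With last doses at Day 28 and Day 336 plus 30 days, the fraction is 58/366 and r = 0.01656. The PK column is then 7.9% or 5.8%, and the Safety column 9.3% or 8.6%.

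Without the constant-hazard assumption, r can lie anywhere from 0 to p. At r = 0 the PK column is 7.5% or 5.0% and the Safety column 9.2% or 8.3%. At r = p every column is 10% and there is no dilution.

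If all 20 PK subjects chose 4 weeks, the PK column would no longer be mixed. It would be a clean 4-week figure, and only the Safety column would combine durations.

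**The case against.** Most of the opposing case concerns the analysis items, and a good part of it stands.

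- Section 12.8 assigns all analyses to a separate SAP, and the summary of changes says some edits were made to agree with it. A SAP therefore existed and may already handle Day 28 and the two durations. This stands. It does not reach the collection conflict, which a SAP cannot cure.
- The non-PK column, about 40 subjects, is untouched and matches the synopsis target of about 40 evaluable subjects treated for 48 weeks. This stands. A reader might infer that the 48-week safety objective is compromised, or that precision should be judged against 60 subjects at 48 weeks. The protocol never promises 60 at 48 weeks, so neither inference is supported.
- A reader might infer that 52-week PK subjects appear in no unmixed safety table. That is too broad: Week 48 laboratory change, the Week 12–48 vital sign tables and the by-visit skin reaction rows after Day 29 can contain only subjects who stayed. The mixing applies to TEAE and SAE counts.
- A reader might also infer that Day 28 vital signs would not be summarised at all. The synopsis does commit to every visit, so the fault is a conflict, not an absence.
- Equal, constant hazard fits the design poorly. PK subjects treat all 10 toenails and adjacent skin for 28 days (9.4), and three of the four common reactions named in Section 5 are application-site events. Early events would shrink the dilution. This stands, and is why the figures are only illustrative.
- AE listings carry start and stop dates, so a Day 1–29 view can be rebuilt. True, but a reader of the summary tables would not see it.
- Section 11.1.10 defines completion only by Week 52. However, Table 1 (including footnote b), 11.1.1 and 11.1.4 already distinguish the planned Day 29 exit from early termination. The gap is editorial.

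**Conclusion.** The concern holds, in three parts of unequal weight.

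The collection conflict is certain on the text and needs no assumption: the synopsis and Table 1 disagree with 11.1.3 and 11.2.3 on Day 28 vital signs. The loss is possible, not established, because a site working from Table 1 would take them.

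The summary gap is also visible in the text, but it is limited to a conflict over vital sign visits and one unspecified laboratory change summary.

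The TEAE mixing is real in structure but unknown in size. It rests on an unstated number of 4-week subjects and on event timing. The illustrative figures for 5 or 10 early exits, at an assumed 10% risk, run from no dilution to a PK column of 7.5% or 5.0% and a Safety column of 9.2% or 8.3%.

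The last two parts are conditional on the SAP, which was not supplied. The changes should be made, but none of this undermines the 48-week safety evidence in the non-PK population.

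**What to change.** - **Collection.** Reconcile the Visit 3 lists in 11.1.3 and the schedule in 11.2.3 with the synopsis and Table 1 on Day 28 vital signs. Reconcile the laboratory sentences in the synopsis Methodology paragraph and in 11.2.2 with the synopsis evaluation criteria, 7.2 and Table 1.
- **Summaries.** Reconcile 12.1.4 with the synopsis on the visits summarised. Add Day 28 change from baseline for 4-week PK subjects in 12.1.3 and 12.1.4.
- **TEAEs and SAEs.** In 12.1.1, split the PK column by consented duration, and add a full-period column for all subjects on the 48-week plan (non-PK plus 52-week PK).
- **Editorial.** Add a sentence to 11.1.10 for the planned Day 29 exit.

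If the SAP already contains the second and third items, align the protocol text with it instead.

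The cost is wording plus a few descriptive tables. The PK split has at most about 20 subjects across both parts, so its percentages will be coarse. No data are needed beyond those the synopsis and Table 1 already schedule.

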7.2 Summary of Study Design

This is an open label, single-arm study designed to evaluate the safety and PK of a once daily topical application of efinaconazole in the treatment of pediatric subjects with mild to severe onychomycosis of the toenails. The study will include a total of 60 subjects, 40 of whom will be 6 to 16 years of age, inclusive, and PK assessments will be performed on approximately 20 subjects 12 to 16 years of age, inclusive (referred to throughout the protocol as the PK subset). All subjects must have onychomycosis of at least 1 great toenail; subjects in the PK subset must have onychomycosis of both great toenails and at least 4 other toenails. Efforts will be made to enroll subjects into the PK subset such that the subjects are evenly distributed across the required age range.

For subjects not participating in the PK subset, the study will consist of 14 scheduled visits, including Screening (up to Day -42), Baseline (Day 1), 12 treatment visits (Weeks 4, 8, 12, 16, 20, 24, 28, 32, 36, 40, 44, and 48), and a 4-week post-treatment follow-up visit (Week 52).

Subjects included in the PK subset MUST decide at time of consent whether to participate in the 4-Week trial, attend the scheduled visits up to Week 4 (Day 29) for collection of the final PK sample and exit the study OR participate in the 52-Week trial treatment through week 48 with additional visits at Weeks 8, 12, 16, 20, 24, 28, 32, 36, 40, 44, and 48), and a 4-week post-treatment follow-up visit (Week 52). The PK assessments will be performed under maximal use conditions.

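### The Safety and PK adverse-event columns pool 4-week-only PK subjects with subjects treated for 48 weeks, and can understate 48-week incidence

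*Combined protocol and SAP*

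**What the plan says.** Section references are to the latest protocol version in the file, the one followed by the summary of changes.

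- **Two durations.** Section 7.2: "Subjects included in the PK subset MUST decide at time of consent whether to participate in the 4-Week trial" or in the 52-week trial. Section 11.1.1 offers the choice going forward: "Newly screened PK subjects will decide at the time of signing consent whether they will consent to the 4-Week trial". The note in 11.1.4 (Visit 3A) adds: "PK subjects who consented to only the 4 Week trial will exit the study on Day 29". Non-PK subjects, and PK subjects who chose 52 weeks, are treated to Week 48 and seen at Week 52.
- **Populations.** Section 12.8.1: "All subjects who receive at least 1 confirmed dose of study drug will be included in the safety population". PK-subset subjects who are dosed "and have any PK data on Days 28 and 29 will be included in the PK population". Neither definition refers to consented duration. The Non-PK population excludes the whole PK subset.
- **Counting.** Section 12.1.1: "All TEAEs will be summarized by the number of subjects reporting each TEAE". It gives the columns and the counting rule as "the relationship to study drug for the safety, PK, and non-PK populations. Each subject will be counted only once", which applies per term.
- **Collection window.** Section 11.3.1.4 collects adverse events "until the last study visit or discontinuation from the study". Serious events must be reported to the sponsor until at least 30 days after the last dose.
- **Skin reactions.** Section 12.1.2 tabulates scores at each visit, and also the worst and last score over the whole post-baseline period.
- **Interim.** Section 12.7 repeats all tables and listings at a date the sponsor will choose.

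Section 12 names no person-time, no summary of treatment duration and no split by consented duration. Section 12.8 refers to a separate SAP for all analyses, and its text is not in the file.

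**The concern.** Safety over 48 weeks is a primary objective (Section 6). A subject who leaves on Day 29 has had about one twelfth of the treatment time of a 48-week subject, yet counts as one full subject in the denominator. A Safety-column percentage read as incidence over 48 weeks would then be too low. The PK column is the more exposed, because all 4-week-only subjects sit in it. It is also the group with the heaviest application on Days 1 to 28: all 10 toenails and the adjacent skin (Section 9.4).

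No single column in 12.1.1 contains exactly the subjects consented to 48 weeks. Safety adds the 4-week-only subjects, and Non-PK omits the 52-week PK subjects. The pooling follows from the stated population and column definitions, not from silence in the text.

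The worst score in 12.1.2 has the same feature. It is the worst of 2 post-baseline visits (Visits 3 and 3A) for a 4-week-only subject, against 13 for a Non-PK subject (12 visits from Week 4 to Week 48, plus Week 52).

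**Working it through.** The plan gives no TEAE rate, power or derived sample size, so there is no figure of its own to reproduce. The check is how far pooling moves the columns.

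**Inputs from the protocol**
- About 60 subjects, about 20 in the PK subset, so about 40 Non-PK (Section 12.8.2).
- Treatment: 4 × 7 = 28 days or 48 × 7 = 336 days, ratio 28/336 = 1/12.

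**Assumptions, not in the documents**
- m, the number of 4-week-only PK subjects, from 0 to 20.
- R, the 48-week risk of at least one TEAE, taken as 30% in every subject.
- No dropout.

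**Formulas**, with r4 the 28-day risk:
- PK column = [(20 − m)R + m·r4]/20
- Safety column = [(60 − m)R + m·r4]/60
- Non-PK column = R

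**Constant hazard.** r4 = 1 − (1 − 0.30)^(1/12) = 2.9%.
- m = 10, PK: (10 × 30 + 10 × 2.93)/20 = 16.5%
- m = 10, Safety: (50 × 30 + 10 × 2.93)/60 = 25.5%

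**Early risk, half of the 30% in the first 28 days.** r4 = 15%.
- m = 10, PK: (10 × 30 + 10 × 15)/20 = 22.5%
- m = 10, Safety: (50 × 30 + 10 × 15)/60 = 27.5%

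| m | PK, constant | PK, early | Safety, constant | Safety, early | Non-PK |
|---|---|---|---|---|---|
| 0 | 30.0% | 30.0% | 30.0% | 30.0% | 30.0% |
| 10 | 16.5% | 22.5% | 25.5% | 27.5% | 30.0% |
| 20 | 2.9% | 15.0% | 21.0% | 25.0% | 30.0% |

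If all first events fell in the first 28 days, r4 = R and every column would read 30% at any m.

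**Other values of R**, constant hazard, m = 10: R = 10% gives PK 5.4% and Safety 8.5%; R = 50% gives PK 27.8% and Safety 42.6%. Using the adverse-event windows (29 and 364 days) in place of treatment days changes these results by no more than 0.2 points.

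**Treated subject-days, Safety population:** 60 × 336 = 20,160 at m = 0; 50 × 336 + 10 × 28 = 17,080 at m = 10; 40 × 336 + 20 × 28 = 14,000 at m = 20.

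**Would a rate per subject-month repair it?** Take the early-risk case, a month of 28 days and first events only.
- First month: hazard −ln(0.85) = 0.1625, time at risk 0.15/0.1625 = 0.92 months.
- Next 11 months: hazard ln(0.85/0.70)/11 = 0.01765, time at risk 0.15/0.01765 = 8.50 months.
- 4-week-only subjects: 0.15/0.92 = 16.3 per 100 subject-months.
- 48-week subjects: 0.30/(0.92 + 8.50) = 3.2 per 100 subject-months.

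The rates differ about fivefold although the two groups have identical risk day by day. A rate can therefore mislead in the other direction.

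**The case against.** The strongest reply is that an undiluted column already exists. The synopsis counts the safety objective as met with about 40 evaluable subjects treated for 48 weeks. Planned Non-PK enrollment is about 40, and 12.1.1 tabulates that group separately. The by-visit skin tables give a time-matched Week 4 view, the by-subject listing carries event dates, and disposition is summarized for each population. No hypothesis is tested and no PK versus Non-PK contrast is planned. All of this stands, and it keeps the point minor. It does not correct the two pooled columns or the pooled worst score.

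Four further objections also stand in part.

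- **m is unknown.** A reader might infer that a third of the Safety population is planned for 28 days. The documents do not support that. The choice is the subject's and is offered to newly screened PK subjects. Under the preceding protocol version the PK subset continued to Week 48. So m = 20 is an extreme bound, and at m = 0 nothing is distorted.
- **Timing matters.** A reader might take the PK/Non-PK ratio at m = 10 as 16.5/30 = 0.55. That rests on constant hazard. With half the risk early it is 22.5/30 = 0.75, and the heavier application on Days 1 to 28 makes early risk plausible.
- **Serious events have a longer window.** For a 4-week-only subject last dosed on Day 28, reporting runs to about Day 58. The 29-day limit applies to non-serious events.
- **The SAP is not available.** The summary of changes says 12.1.1 was edited to agree with SAP wording, so SAP text on TEAEs existed. It may hold an exposure table or a duration split.

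Section 12.1.1 also speaks of numbers of subjects, not percentages. Percentages of each population are the expected presentation, but that is a reading.

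**Conclusion.** The concern holds conditionally. If at least one PK subject takes the 4-week option, and some first events would occur after Day 28, the Safety and PK TEAE columns understate 48-week incidence. The whole-study worst score has the same defect. At m = 10 and an assumed 48-week risk of 30%, the PK column reads 16.5% to 22.5% and the Safety column 25.5% to 27.5%, depending on whether the hazard is constant or half the risk is early. The figures also assume equal risk in all subjects and no dropout.

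The documents do not support saying that the columns will certainly be lowered, that the PK group will appear safer solely because of short follow-up, or that 48-week incidence cannot be read from the planned tables: the Non-PK column supplies it for about 40 subjects. Nor can it be said that the SAP leaves this unaddressed. The effect is on descriptive summaries only. Severity: minor.

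**What to change.** In 12.1.1 and the matching synopsis text, and for the worst score in 12.1.2:

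1. Split the PK column into 4-week-only and 52-week subjects.
2. Report 48-week incidence in subjects consented to 48 weeks, that is, Non-PK plus 52-week PK.
3. For any PK versus Non-PK comparison, use events with onset in Days 1 to 29 in both groups.
4. Show treated subject-days for each column.

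Apply the same to the interim tables, where exposure may also be incomplete in other subjects. Do not make a rate per subject-month the main remedy, for the reason shown in the working.

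The cost is two or three sentences and one or two extra tables. Consented duration, application diaries and event onset dates are already collected. The downside is small counts in the 4-week-only column. If the SAP already contains these displays, a cross-reference in 12.1.1 is enough.
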